- a. **Data collection and storage:** Data collection and storage will be conducted according to standardized protocols. All research data collection and storage will be managed by Yale personnel who have received the proper training by Yale to ensure that research is in compliance with the current applicable laws, regulations and Yale's policies and procedures in support of the protection of research participants. All research personnel are required to participate in and document training in protection of human subjects and the responsible conduct of scientific research. Only authorized research personnel will have access to the information gathered in this study. All study data will ultimately reside on Yale encrypted computers. Quantitative data will be entered into a password-protected SPSS database housed on Yale encrypted computers. The organizational structure used to ensure quality of data in this study include: (a) preliminary review of all data for completeness and coding errors by the PI; and (b) utilization of error-checking statistical procedures. All information will be identified by code and will not be linked to personally-identifying information. Patient names or other identifiers such as social security number, initials, birth date will not be used to identify any records. Only a code number will identify the individual research records. The code number will not be based on any information that could be used to identify the subjects (for example, social security number, initials, birth date, etc.). The master list linking names to code numbers will be kept separately from the research data on Yale encrypted computers. Only approved members of the research team will have access to personally-identifying information (e.g., phone numbers, addresses). This information will be stored separately on Yale encrypted computers.
- b. **App data:** App data is collected, managed and stored according to standardized protocols at Somatix, Inc. Data is collected from the smartphone app to the Somatix backend platform and to the database running over Hypertext Transfer Protocol for secure communication (HTTPS). All data is stored on Amazon Web Services (AWS) - Cloud Computing, Relational Database Service (Amazon RDS) for MySQL, secured using Amazon's advanced capabilities. Any personal-identifying information (e.g., location) will be encrypted in the database. Only authorized Somatix, Inc. personnel will have access to this database. The database will only be accessed by Somatix's password-protected computers. The participant will be identified only by a fake phone number in Somatix database. Somatix will not have access to the key linking a participant's personal information (real phone number) to this fake phone number. Only

the fake phone number will be associated with the participant's data in the Somatix database.

3. How will the digital data be stored? CD DVD Flash Drive Portable Hard Drive Secured Server
 Laptop Computer Desktop Computer Other AWS
4. What methods and procedures will be used to safeguard the confidentiality and security of the identifiable study data and the storage media indicated above during and after the subject's participation in the study?

Data collection and storage will be conducted according to standardized protocols. All research personnel are required to participate in and document training in protection of human subjects and the responsible conduct of scientific research. All information will be identified by code and will not be linked to subject name except as described above. All data analyses will be performed under approved HIC protocols. Hardcopies of the questionnaires without identifying information will be stored in a locked file cabinet in the study office. All storage media will be password protected using Yale approved protocols.

To ensure that the Somatix, Inc., securely maintain the study data, we have obtained the required Security Design Review (SDR) by Yale's Information Security Department and establish a Business Associate Agreement between Yale's HIPAA Privacy Office and Somatix, Inc. The SDR process ensures that the security and application of systems are in line with best practices and standards at Yale.

All portable devices must contain encryption software, per University Policy 5100. If there is a technical reason a device cannot be encrypted please submit an exception request to the Information Security, Policy and Compliance Office by clicking on url <http://its.yale.edu/egrc> or email [contact]

5. What will be done with the data when the research is completed? Are there plans to destroy the identifiable data? If yes, describe how, by whom and when identifiers will be destroyed. If no, describe how the data and/or identifiers will be secured. *Write here*

Data collected in the study will reside in our electronic storage mechanism for 7 years. All data analyses (deidentified and coded as described above) will be performed under approved HIC protocols.

6. If appropriate, has a Certificate of Confidentiality been obtained?

This project has NIH funding (1R34AT010365-01) and therefore a CoC was automatically issued in accordance with NIH CoC Policy (NOT-OD-17-109).

SECTION V: POTENTIAL BENEFITS

Potential Benefits: Identify any benefits that may be reasonably expected to result from the research, either to the subject(s) or to society at large. (Payment of subjects is not considered a benefit in this context of the risk benefit assessment.)

By participating in this research participants will receive free smoking cessation technology (smartband, smartphone app). By offering free quitting strategies, this study may help to engage more smokers into treatment, thus reducing the enormous health care costs and loss of lives associated with cigarette smoking.

SECTION VI: RESEARCH ALTERNATIVES AND ECONOMIC CONSIDERATIONS

1. **Alternatives:** What other alternatives are available to the study subjects outside of the research? Alternatives to treatment in this study are currently approved over the counter smoking cessation treatments such as the nicotine patch, nicotine gum, and nicotine lozenge. Subjects may get prescriptions from their physicians for varenicline, bupropion, the nicotine nasal spray, or the nicotine inhaler. Subjects will be recommended to use quit smoking medications while participating in this study.
2. **Payments for Participation (Economic Considerations):** Describe any payments that will be made to subjects, the amount and schedule of payments, and the conditions for receiving this compensation. Study compensation will be: \$10 upon completion of the zoom/online training, \$20 upon completion of the second study survey, and \$10 upon completion of the third study survey. At the end of the study, they will be paid \$1 per day for each day of the 60-day study that they have worn their smartband for 12 waking hours (up to \$60). At the end of the study, they will also be paid \$10 for the end of study survey, and a \$50 bonus payment if they have completed all parts of the study. **Total study payment will be up to \$160** (up to \$40 paid upon each survey completion, up to \$120 paid at the end of the study). Please note that all study equipment (smartband, CO-monitor, saliva kit if applicable) must be returned before the final study payment. Finally, they may be invited to take part in an optional debriefing at the end of the study, for which they will be paid an additional \$10. Study payments will be by amazon.com gift card.
3. **Costs for Participation (Economic Considerations):** Clearly describe the subject's costs associated with participation in the research, and the interventions or procedures of the study that will be provided at no cost to subjects. To participate in the study, participants will be required to already own a smartphone.
4. **In Case of Injury:** This section is required for any research involving more than minimal risk, and for minimal risk research that presents the potential for physical harm (e.g., research involving blood draws).
 - a. Will medical treatment be available if research-related injury occurs? *Write here*
 - b. Where and from whom may treatment be obtained? *Write here*
 - c. Are there any limits to the treatment being provided? *Write here*
 - d. Who will pay for this treatment? *Write here*
 - e. How will the medical treatment be accessed by subjects? *Write here*

This protocol is deemed to be of minimal risk. If subjects develop a mental or physical problem as a result of involvement in this study, they will seek their own treatment independently from the study. The subject's insurance carrier will be expected to pay the costs of such treatment. No financial compensation is available for this treatment.

IMPORTANT REMINDERS

Will this study have a billable service? Yes No

A billable service is defined as any service rendered to a study subject that, if he/she was not on a study, would normally generate a bill from either Yale-New Haven Hospital or Yale Medical Group to the patient or the patient's insurer. The service may or may not be performed by the research staff on your study, but may be provided by professionals within either Yale-New Haven Hospital or Yale Medical Group (examples include x-rays, MRIs, CT scans, specimens sent to central labs, or specimens sent to pathology). Notes: 1. There is no distinction made whether the service is paid for by the subject or their insurance (Standard of Care) or by the study's funding mechanism (Research Sponsored). 2. This generally includes new services or orders placed in EPIC for research subjects.

If answered, "yes", this study will need to be set up in OnCore, Yale's clinical research management system, for Epic to appropriately route research related charges. Please contact [contact]

Are there any procedures involved in this protocol that will be performed at YNHH or one of its affiliated entities?

Yes No

If Yes, please answer questions a through c and note instructions below.

- a. Does your YNHH privilege delineation currently include the **specific procedure** that you will perform? Yes No
- b. Will you be using any new equipment or equipment that you have not used in the past for this procedure? Yes No
- c. Will a novel approach using existing equipment be applied? Yes No

If you answered "no" to question 4a, or "yes" to question 4b or c, please contact the YNHH Department of Physician Services ([name]) for prior approval before commencing with your research protocol.

IMPORTANT REMINDER ABOUT RESEARCH AT YNHH

Please note that if this protocol includes Yale-New Haven Hospital patients, including patients at the HRU, the Principal Investigator and any co-investigators who are physicians or mid-level practitioners (includes PAs, APRNs, psychologists and speech pathologists) who may have direct patient contact with patients on YNHH premises must have medical staff appointment and appropriate clinical privileges at YNHH. If you are uncertain whether the study personnel meet the criteria, please telephone the Physician Services Department at [contact]. **By submitting this protocol as a PI, you attest that you and any co-investigator who may have patient contact has a medical staff appointment and appropriate clinical privileges at YNHH.**

References

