
Aim 1. To determine treatment fidelity for a smartband/smartphone-based mindfulness intervention. Fidelity measures will be: (1) percent of smoking episodes correctly detected and rate of false alarms; (2) percent of "mindful smoking" exercises correctly triggered by smoking and rate

of false alarms; and (3) users' real time ratings of how timely "RAIN" was delivered to predicted smoking episodes, measured as % of participants and score range (very low, low, moderate, high, very high), with feasibility determined by 75% of participants rating timeliness as moderate or higher. We expect to replicate previous findings of >80% detection and negligible false alarms [14] and to find moderate or higher timeliness ratings. These and other aspects of treatment fidelity will be reported according to recommended guidelines [17].

Aim 2. To determine adherence to a smartband/smartphone-based mindfulness intervention.

Adherence measures will be: (1) percent of time spent wearing the smartband; (2) percent of smoking notifications answered; (3) percent of ecological momentary assessment (EMA) ratings (e.g., timeliness, helpfulness, craving, affect) answered; and (4) percent of mindfulness exercises completed. We expect high response rates based on our earlier studies of smartband-based smoking notifications [14] and EMA of craving and other factors [5]. Adherence cut-offs (e.g., time spent wearing the smartband) will be 80%. Adherence was high in pilot work (90% of participants answered 80% of smoking notifications[14]).

Aim 3. To determine the acceptability of a smartband/smartphone-based mindfulness intervention.

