Quit is defined based on proposed standards [73] as 7 day point prevalence abstinence and continuous abstinence (<5 cigs since quit date). E-cigarette use will not constitute a relapse but will be monitored and reported. Ratings (Likert items, e.g., timeliness) will be evaluated as % of participants and score range (very low, low, moderate, high, very high), with feasibility determined by 75% of participants rating an item as moderate or higher (Aim 1,3). Average responses for a given factor (e.g., satisfaction) on the User Experiences Questionnaire will be tested similarly, and qualitative analysis of open-ended questions will be used to further evaluate acceptability (Aim 3). Adherence cut-offs (e.g., time spent wearing the smartband) will be 80% (Aim 2). Adherence was high in pilot work (90% of participants answered 80% of smoking notifications[14]).

D.5. Assessments

Participants will be provided links to online surveys at baseline, 21 days, 30 days and 60 days (end of study) to measure smoking and other domains ([Table 1](#)) and to provide study instructions including initial mindfulness training (15 min). All surveys will be hosted on Yale Qualtrics secure survey software (<https://yalesurvey.qualtrics.com>) and optimized for delivery on mobile devices. The baseline survey will be automatically provided to eligible participants upon completing the screening survey and providing informed consent. All following surveys will be automatically emailed to the participant at each time point. For non-completed surveys a reminder text message will be sent at 1 and 2 days, followed by a phone call at 3 days. Demographics and smoking characteristics will be evaluated using standardized PhenX Toolkit protocols. Smoking status will include one-week point prevalence abstinence and continuous abstinence [73], cigarettes per day, and other tobacco use (e.g., e-cigarettes). All are standardized measures with documented psychometrics. In addition, across treatment, ratings are delivered as EMA after each mindfulness exercise and include helpfulness, timeliness, craving and affect. At the end of the study, active participants may be asked to take part in an optional debriefing to provide feedback about their experiences in the study.

Table 1. Assessments.

Instrument Name	Domain assessed	Baseline	Day 21	Day 30	Day 60
Demographics	Demographics	X			
Smoking status [73]	Smoking	X	X	X	X
Time Line Follow Back [74] (since last survey)	Daily smoking	X	X	X	X

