For the subsequent 30 days, the RAIN exercise will be automatically delivered to the user via the smartphone app prior to each predicted smoking episode according to individual smoking profiles obtained as described below. They will first be asked to rate their craving (“How much are you craving a cigarette?” VAS “very much” to “not at all”) and affect (“How are you feeling?” VAS “very bad” to “very good” ¹⁰⁵). Next, they will be prompted to complete the RAIN exercise, also delivered as a 2-minute audio-guided mindfulness practice with subtitles. After completing RAIN, they will be asked “How helpful did you find this exercise?” (VAS “very helpful” to “not at all”); “How was the timing of this exercise?” (VAS “too early” to “too late”); and to again rate their craving and affect.

D.9. Individualized smoking profiles

Individualized smoking profiles will be obtained using smartband data tracking smoking across the first 21 days of the study, based on the maximum information possible: (1) average times each cigarette is smoked each day; (2) average times each cigarette is smoked on weekdays versus weekends; (3) average time between cigarettes; (4) average wake/sleep time; and (5) average cigarettes per day each day. Less predictable smokers will have less data to inform the prediction algorithm. At the very least, their waking hours will be divided by the number of cigarettes smoked per day and a prompt will be sent at random times in each interval. How much smartband tracking data is needed to adequately develop an individualized smoking profile is a main question in this feasibility trial. We will use this data to then deliver RAIN to the user for 30 days after their quit date. RAIN will be delivered 5 minutes prior to each predicted smoking episode during waking hours.

D.10. Adherence

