In the unlikely event that such events occur, serious and unanticipated and related adverse events or unanticipated problems involving risks to subjects or others will be reported immediately (if possible), followed by a written report within 7 calendar days of the Principal Investigator becoming aware of the

event to the Yale IRB, Independent Monitoring Monitor(s), and NCCIH. Any other unanticipated problem will be reported to the IRB, Independent Safety Monitor(s), and NCCIH within 14 days of the PI becoming aware of the problem.

To ensure that the design, conduct, and reporting of research for this project is free from bias resulting from Investigator financial conflicts of interest, the project will be conducted in accordance with NIH Financial Conflict of Interest (FCOI) regulation, *Responsibility of Applicants for Promoting Objectivity in Research for which PHS Funding is Sought* (42 CFR Part 50 Subpart F), applicable to grants and cooperative agreements (2011 Revised Regulations) and Yale University Policy on Conflict of Interest.

13. Statistical Considerations: Describe the statistical analyses that support the study design.

Overview: Quit is defined based on proposed standards [73] as 7 day point prevalence abstinence and continuous abstinence (<5 cigs since quit date). E-cigarette use will not constitute a relapse but will be monitored and reported. Ratings (Likert items, e.g., timeliness) will be evaluated as % of participants and score range (very low, low, moderate, high, very high), with feasibility determined by 75% of participants rating an item as moderate or higher. Average responses for a given factor (e.g., satisfaction) on the User Experiences Questionnaire will be tested similarly, and qualitative analysis of open-ended questions will be used to further evaluate acceptability. Adherence cut-offs (e.g., time spent wearing the smartband) will be 80%. Adherence was high in pilot work (90% of participants answered 80% of smoking notifications [14]).

Aim 1. To assess treatment fidelity for a smartband/smartphone-based mindfulness

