intervention: (1) Whether we can accurately detect smoking episodes will be determined by the percent of smoking episodes detected and the rate of false alarms in the first 21 days of the study during which smokers are wearing the smartband to track smoking and upon smoking detection are asked to confirm or deny smoking and self-report any undetected smoking episodes. We expect to replicate previous findings of >80% detection and negligible rate of false alarms [14]. (2) Whether we can deliver mindful smoking triggered by smoking episodes will be determined by the percent of mindful smoking exercises correctly triggered by detected smoking episodes and the rate of false alarms in the next 7 days of the study during which any detected smoking episode triggers a prompt that first asks the smoker to confirm or deny smoking and then launches the mindful smoking exercise. Again, we expect to replicate previous findings of >80% detection and negligible rate of false alarms [14]. (3) Whether we can deliver RAIN to predicted smoking episodes will be measured as average timeliness ratings in the next 30 days of the study during which RAIN is delivered prior to predicted smoking episodes and the smoker is asked to rate whether the exercise was delivered on time. Additionally, we will analyze the craving ratings obtained before participants complete RAIN, as a proxy for whether or not we have targeted moments of high craving. Ratings (Likert items for timeliness, craving) will be evaluated as % of participants and score range (very low, low, moderate, high, very high), with feasibility determined by 75% of participants rating an item (timeliness, craving) as moderate or higher. We expect on average moderate to high timeliness and craving ratings, suggesting that RAIN was delivered in time to help cope with cravings. These and other aspects of treatment fidelity will be reported according to recommended guidelines [17].

Aim 2. To assess adherence to a smartband/smartphone-based brief mindfulness intervention:

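### The RAIN timing scale runs from too early to too late, but the 75% feasibility rule treats it as low to high, so a pass does not show on-time delivery

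*Combined protocol and SAP*

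**What the plan says.** Section D.8.c collects RAIN timing on a visual analog scale: "How was the timing of this exercise?” (VAS “too early” to “too late". The scoring is described in four other places.

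- **Opening statement of aims, Aim 1, measure 3:** timeliness is graded in five levels from very low to very high, "with feasibility determined by 75% of participants rating timeliness as moderate or higher".
- **Section D.4, Outcomes:** "Ratings (Likert items, e.g., timeliness) will be evaluated as % of participants and score range (very low, low, moderate, high, very high").
- **Section 13, Overview:** the same five levels, "with feasibility determined by 75% of participants rating an item as moderate or higher".
- **Section 13, Aim 1:** delivery of RAIN to predicted episodes "will be measured as average timeliness ratings in the next 30 days of the study". It continues: "Ratings (Likert items for timeliness, craving) will be evaluated as % of participants and score range", "with feasibility determined by 75% of participants rating an item (timeliness, craving) as moderate or higher". Moderate-to-high timeliness and craving ratings are then read as "suggesting that RAIN was delivered in time to help cope with cravings".

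No section says which end of the timing line is high, how the line maps to five levels, or what counts as on time. The item is a visual analog scale in D.8.c and a Likert item in D.4 and section 13.

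**The concern.** A cut of 'moderate or higher' has meaning only when more is better. Helpfulness runs from not at all to very helpful and craving from not at all to very much, so each needs at most a reversal. The timing line has a failure at both ends, and reversing it only changes which failure scores highest.

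Averaging adds a second fault. A participant whose prompts arrive sometimes far too early and sometimes far too late can average near the middle and look well served. Such mixed errors are possible here, because section D.9 falls back on randomly timed prompts within intervals for smokers whose pattern is hard to predict.

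This is the named feasibility criterion for delivering RAIN ahead of predicted smoking, and section D.1 says the results are to inform a larger efficacy trial. A false pass would carry a mistimed delivery method into that trial as if it had been shown to work.

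**Working it through.** **The plan's figure.** The 75% is a set threshold with no derivation, so there is nothing to reproduce. The check is what the rule can and cannot separate.

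**Step 1. Direction, without numerical assumptions.** Let x run from 0 (too early) to 100 (too late), with 50 on time. If the score rises with x, 'moderate or higher' means x ≥ c, and this always includes x = 100. If it falls with x, the rule means x ≤ c′, and this always includes x = 0. No cut-point and no reversal removes the bad extreme on the passing side.

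**Step 2. Counting example, 100 participants, cut at 40.**

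- 60 participants at 95, 15 at 50, 25 at 5. With late high, 60 + 15 = 75 pass, so the 75% criterion is met with 15 on time. With early high, 15 + 25 = 40 pass.
- 75 participants at 95 and 25 at 5. With late high, 75 pass and the criterion is met with nobody on time.

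**Step 3. Cancellation.** Half of one person's ratings at 5 and half at 95 give a mean of (5 + 95)/2 = 50, which passes under either coding, although every rating is 45 points from on time. Folding only the mean does not help, since |50 − 50| = 0. Each rating must be folded before averaging.

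**Step 4. Size, for illustration.** Assumptions not in the documents: 0–100 line; five equal bands, so moderate starts at 40; participant means; k = 30 to 150 ratings each. The upper figure is 5 per day (the entry minimum for cigarettes per day) × 30 days; 30 allows for skipped exercises. Ratings have mean μ and within-person SD σ; participants differ with SD b. Ignoring clipping at the ends of the line,

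P(pass, late high) = Φ((μ − 40)/√(b² + σ²/k)).

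With k = 60:

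- On time (50, SD 15), b = 10: √(100 + 225/60) = 10.19; 10/10.19 = 0.98; Φ = 0.84.
- Half near 10 and half near 90 (SD 5 within each), b = 0: σ = √(40² + 5²) = 40.3; 40.3/√60 = 5.20; 10/5.20 = 1.92; Φ = 0.97.
- Evenly spread, b = 0: σ = 100/√12 = 28.9; 28.9/√60 = 3.73; 10/3.73 = 2.68; Φ = 0.996.
- Late (85, SD 10), b = 10, early high: the mean must be at most 60; (60 − 85)/√(100 + 100/60) = −2.48; Φ = 0.007.

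Simulation with clipping gives the following shares of participants passing, over k = 30 to 150. The last two columns apply one example of a folded rule: more than half of a participant's ratings in the middle third of the line.

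| Ratings | Plan's rule, b = 0 | Plan's rule, b = 10 | Middle third, b = 0 | Middle third, b = 10 |
|---|---|---|---|---|
| On time (50, SD 15) | 100% | 83–84% | 99–100% | 84–88% |
| Late (85, SD 10), late high | 100% | 100% | 0% | 3–4% |
| Late (85, SD 10), early high | 0% | about 1% | 0% | 3–4% |
| Evenly spread | 97–100% | 82–85% | 0–2% | 0–2% |
| Half near 10, half near 90 | 91–99.9% | 81–86% | 0% | 0–0.2% |

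Early ratings (15, SD 10) mirror the late rows.

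**Step 5. The folded columns by hand, b = 0, k = 60.** The chance that one rating lies in the middle third (33.3 to 66.7) is p = 2Φ(16.67/15) − 1 = 0.733 for the on-time group, so more than 30 of 60 is near certain. For evenly spread ratings p = 1/3, and the binomial chance of more than 30 of 60 is 0.3%.

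**The case against.** The strongest reply is that the plan leaves the mapping unstated and does not write down a wrong one. It names the construct as how timely RAIN was, so a 'very high' score could mean close to on time and a fold may be intended. That is possible, but it is not written. The text applies a low-to-high scale, an average and a cut to an item whose high end is a failure. Leaving the choice until the data are in would let the coding decide the result.

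Second, other measures bear on the question. Pre-RAIN craving has its own 75% criterion, and the User Experiences Questionnaire has a timeliness rating. Reporting the five-level distribution could also show a pile-up at one end. These limit the harm. But craving is described as a proxy, the questionnaire item serves acceptability under Aim 3, and a distribution of participant averages would not reveal cancellation within a person.

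Third, this is a feasibility study and timeliness is one of three fidelity measures. That is true, but feasibility is what the trial sets out to establish.

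Two narrower points stand. Section 13 does not say whether averaging is per participant, so cancellation within a person rests on that reading. The documents also do not say how many participants will receive randomly timed prompts, so mixed errors are possible rather than shown to be likely.

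**Conclusion.** The concern holds. The timeliness criterion is wrong as written and should be corrected before analysis. That one direction of consistent mistiming passes follows from the anchors and the direction of the rule, and needs no assumption about bands or spread. The percentages do rest on the assumed line, bands, spreads and participant means. With a between-person SD of 10, the rule scores erratic timing about the same as good timing (81–86% against 83–84%) and scores one direction of consistent mistiming above it (100%). The timeliness rating therefore cannot support the planned reading that RAIN arrived in time. The companion measures soften this but do not repair the criterion.

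**What to change.** Keep the visual analog scale and amend the timing rule in Aim 1, section D.4 and section 13 (Overview and Aim 1), for this item only. Possible wording:

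*Each RAIN timing rating is scored by its distance from the midpoint and is on time if it lies within [band fixed in advance]. For each participant we compute the share of ratings on time. Timeliness is feasible if at least 75% of participants reach [share fixed in advance]. Too-early and too-late shares are reported separately.*

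State which end of the line is coded high. The team should choose the band. The N=10 pilot in section D.1 can show how widely one person's ratings scatter before the band is fixed for the n=100 trial. If the item can still be changed, a one-directional question on how timely the exercise was would also match the written cut, but it would lose the direction of the error.

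The fix changes analysis wording only and needs no new data. The cost is a possibly less favourable figure and a judgement about the band. With the middle-third example:

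- **Wider scatter, centred on time:** with rating SD 20, 81–99% of participants pass with no between-person variation and 62–77% with between-person SD 10. With rating SD 25, 41–42% and 24–30% pass.
- **More variation between people:** in the on-time group with rating SD 15 and 60 ratings each, 70% pass at between-person SD 15, below the 75% threshold.
- **Mildly late ratings (mean 65, SD 10):** 70–94% still pass with no between-person variation and about 55% with SD 10. A second example, mean distance from the midpoint at most 20, is more lenient here. This is why the too-late share must be reported alongside the criterion.
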